7.4.7 Handling of Early Termination Visits and Additional Treatments

Early termination visit data (on or prior to Day 43) for safety variables will be analyzed at the closest scheduled visit. If the closest visit has valid data, the early termination data will be assigned to the next available visit.

Any safety or immunologic data collected for additional treatments (after Day 43) will be summarized as visits separate from the scheduled visits (up to and including Day 43 and End of Study).

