5.2.3 Removal of Patients from Treatment or Assessment

The patients may withdraw from treatment with study product if they decide to do so, at any time and irrespective of the reason, or this may be the Investigator's decision to protect the safety of the patient. All efforts should be made to document the reason for discontinuation and this should be documented in the electronic case report form (eCRF).

Other criteria for possible discontinuation are:

- PSADT < 90 days
- Unacceptable toxicity as judged by the Principal Investigator

Adverse events which are dose-limiting toxicities

Patient is lost to follow-up

Patients will be followed up according to the study procedures as specified in this protocol up to the scheduled date of study completion, or up to recovery or stabilization of a followed-up AE, or the initiation of post study treatment, whichever comes last.

If possible, and after the permanent discontinuation of treatment, the patients will be assessed using the procedure normally planned for the 'end of study'.

The patients may withdraw from the study follow-up schedule, before study completion if they decide to do so, at any time and irrespective of the reason, or this may be the Investigator's decision:

Patients who are lost to follow-up:

- The Investigator should make every effort to re-contact the patient, to identify the reason why he/she failed to attend the visit, and to determine his/her health status, including at least his/her vital status. Attempts to contact such patients must be documented in the patient's records (e.g. times and dates of attempted telephone contact, receipt for sending a registered letter).
- Patients who did not complete the study and for whom no endpoint data are available will be considered as lost to follow-up.

The statistical analysis plan will specify how these patients lost to follow-up for their primary endpoints will be considered.

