5.5.2.3 Dose-escalation Treatment: Day 8 ± 2 days

- Symptom-directed physical examination
- Vital signs
- ECOG score
- Biochemical testing: chemistry, hematology, coagulation, CH50
- Physician administration site assessment
- Adverse events, concomitant medications

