5.5.2.4 Dose-escalation Treatment: Day 15 ± 2 days

- Symptom-directed physical examination
- Vital signs
- ECOG score
- Clinical laboratory tests, chemistry, hematology, coagulation, CH50
- Adverse events, concomitant medications

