5.5.2.5 Study Visits: Day 22, Day 43 ± 3 days

- Immunologic blood collection pre-dose on day of drug administration on Day 22, 43, and every 21 days thereafter if continuing treatment
- Symptom-directed physical examination
- Vital signs and ECG
- Eastern Cooperative Oncology Group (ECOG) performance score
- Prostate-specific antigen (PSA) assessment
- Biochemical testing: chemistry, hematology, coagulation, CH50
- Evaluation of subject to allow continued dose escalation
- Study treatment administration
- Physician administration site assessment (post-administration)
- Adverse events and concomitant medications

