The duration of the study for each patient will include an up to 8-week screening phase, 21day study treatment cycles for 9 cycles and 6 months of follow up including monthly PSAs, and an end of study visit (28 days post last dose of study treatment). Patients may continue to receive single repeated doses of SNS-301 at their original dose level (or at the MTD when it is determined) every 21 days or until the observance of PSA doubling < 90 days or unacceptable toxicity (either for that patient or in their dose cohort).

A complete schedule of procedures and assessments is in Table 4-1.

Assessment	Screen (D-56+7 ^e to D0)	A	Cycle		Cycl	le 2-3	Additional Treatments	Follow- up/End of study
	/	D1	D8 ± 2	D15±2	D22 ± 3	D43 ± 3	Every 21 ± 3 day	Every 28 ± 3 days after final treatment for 6 Months
Signed Informed Consent	X							
HAAH assessment ^a	X				_			
Demographics	Х					•		
Medical/Oncology History	Х							
Tumor Burden Evaluation ^d	Х							
Baseline Signs and Symptoms	Х							
Physical Examination	Х							Х
Symptom-Directed		Х	Х	Х	Х	Х	Х	
Physical Examination		• /\	N .	\wedge				\wedge 1
Vital Signs	X	X	X	X	Х	X	X	/ X
ECOG Performance Score	Х	Х	Х	Х	Х	Х	Х	Х
ECG	Х	Х			Х	Х	Х	Х
PSA	Х	Х			Х	Х	Х	Х
Hematology ^b	Х	Х	Х	Х	Х	Х	Х	
Chemistry ^b	Х	Х	Х	Х	Х	Х	Х	
Coagulation, CH50 ^b	Х	Х	Х	Х	Х	Х	Х	
Study Treatment administration		Х			Х	X	X	
Physician Administration Site Assessment		Х	Х		Х	X	X	
Immunologic Blood Collection ^c		Х			Х	X	Х	Х
Cohort enrollment evaluation					Х			
Concomitant Medications Collection		Х	Х	Х	Х	X	Х	Х
Adverse Events Assessments ^f		Х	Х	Х	Х	X	Х	Х

- a HAAH assessment: following informed consent, archived prostate tumor tissue and patient serum will be tested for the expression of HAAH. Only patients who test positive for HAAH expression in archived tumor tissue (if available) or fresh serum may be continued in the study. HAAH assessments are not subject to the 56-day screening window and are valid for 6 months. Patients who are negative for HAAH may be followed for 6 months and if PSA rises over that period time, they can enroll in the study provided that tissue or fresh serum is positive for HAAH
- b Biochemical testing (chemistry, complete blood count, coagulation, and total complement CH50,) to be obtained within 14 days prior to study drug administration if screening period is between 3 and 8 weeks. PSA levels are also to be evaluated at screening and within 14 days prior to study drug administration if screening period is between 3 and 8 weeks.

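### SAP 7.4.7 lets early-termination safety data move to a later visit with no window limit, so Day 23-32 values can be tabulated as Day 43

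*SAP*

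**What the plan says.** SAP 7.4.7 has a two-step rule. First: "Early termination visit data (on or prior to Day 43) for safety variables will be analyzed at the closest scheduled visit". Then: "If the closest visit has valid data, the early termination data will be assigned to the next available visit". The section does not define which visit counts as available, sets no limit on distance, and provides no separate row for termination data. Additional-treatment data after Day 43 "will be summarized as visits separate from the scheduled visits (up to and including Day 43 and End of Study").

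The relevant visits are in Protocol sections 5.5.2.3 to 5.5.2.5: "Dose-escalation Treatment: Day 8 ± 2 days", "Dose-escalation Treatment: Day 15 ± 2 days" and "Study Visits: Day 22, Day 43 ± 3 days". SAP Table 4-1 repeats them. ECG is not scheduled on Day 8 or Day 15.

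Protocol 5.2.3 says that after permanent discontinuation, where possible, "the patients will be assessed using the procedure normally planned for the 'end of study". Protocol 5.5.2.7 lists those procedures, which include laboratory tests, vital signs, ECG and ECOG, and times the first such visit at 28 ± 3 days after the last treatment.

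**The concern.** A by-visit table tells the reader when a value was measured and, in this trial, how many doses came before it. Under the second sentence of 7.4.7 a value can carry a visit label that is wrong on both counts. A scheduled Day 43 value is taken 43 − 22 = 21 days after the second dose. A patient who stopped after one dose could be shown in that cell.

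The tables exposed are the by-visit summaries through Day 43 in SAP 8.6: laboratory parameters, vital signs, ECG (including its by-visit shift table), ECOG by visit, and site reactions by visit. Biochemical safety is a secondary endpoint, and with so few patients per dose level a single misplaced value is visible in the mean and the change from baseline.

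**Working it through.** The SAP gives no figure to reproduce, so the check applies the rule to the schedule.

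**Inputs.** Scheduled days are 1, 8, 15, 22 and 43 for laboratory tests, vital signs and ECOG, and 1, 22 and 43 for ECG (SAP Table 4-1). Windows are Days 6-10, 13-17, 19-25 and 40-46 (Protocol 5.5.2.3 to 5.5.2.5). Cohorts are 3 or 6 (SAP 7.1). I assume that earlier visits were attended on their nominal day and have valid data, and I read the next available visit as the next later scheduled visit without data.

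**Step 1: where the fallback sends the data.** The closest visit changes at the midpoint between two visits: (22 + 43)/2 = 32.5, (1 + 22)/2 = 11.5, (8 + 15)/2 = 11.5 and (15 + 22)/2 = 18.5.

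| Assessment | Termination day | Closest visit (filled) | Tabulated as | Shift in days |
|---|---|---|---|---|
| Labs, vital signs, ECOG, ECG | 23-32 | Day 22 | Day 43 | 43 − 23 = 20 down to 43 − 32 = 11 |
| ECG | 2-11 | Day 1 | Day 22 | 22 − 2 = 20 down to 22 − 11 = 11 |
| Labs, vital signs, ECOG | 9-11 | Day 8 | Day 15 | 15 − 9 = 6 down to 15 − 11 = 4 |
| Labs, vital signs, ECOG | 16-18 | Day 15 | Day 22 | 22 − 16 = 6 down to 22 − 18 = 4 |

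None of the values moved to Day 43 lies in the Day 40-46 window. Days 23-25 lie inside the Day 22 window and are still moved. If Day 22 is empty, a Day 23-32 value stays at Day 22.

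**Step 2: when a termination visit would fall.** Take the end-of-study timing of 28 ± 3 days after the last dose.
- Last dose on Day 1, with Day 22 attended but no dose given: 1 + 25 = Day 26 to 1 + 31 = Day 32. All of these days are inside 23-32, and the shift is 43 − 26 = 17 down to 11 days. The patient is 25 to 31 days past a single dose.
- Second dose given at Day 22 ± 3: 19 + 25 = Day 44 to 25 + 31 = Day 56. All of these days are beyond the Day 43 limit of 7.4.7, so the rule does not apply.

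The first case is therefore the one the documents best support. An ECG on Days 2-11 would need a termination visit earlier than that timing.

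**Step 3: weight in a cell.** One value is 1/3 = 33% of a mean over 3 patients and 1/6 = 17% of a mean over 6. If the patient left for a non-safety reason in cycle 1 and was replaced (Protocol 5.3.5), the Safety Population still includes him, so a cohort of 3 becomes a cell of up to 4 and the share is 1/4 = 25%. These are weights, not estimates of bias.

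**The case against.** The best objection is that other SAP rules may catch these data first. Section 7.4.6 keeps unscheduled or repeated laboratory results out of continuous summaries, and a second sample on Day 24 could count as a repeat of Day 22. Section 7.4.5 defines an end of treatment phase visit, which could be the same physical visit and is summarized separately under 8.6. Section 7.4.7 itself names End of Study among the scheduled visits, so a withdrawn patient's visit might simply be recorded there. All of this stands as ambiguity: the SAP gives no order of precedence. But 7.4.7 is the only rule written for early termination, so it is the natural one to apply, and the overlap is itself a reason to rewrite it.

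A reader might infer that a value taken two days after the second dose will routinely be shown as Day 43. That is possible only with an ad hoc termination visit. Protocol 5.2.3 fixes the procedures more clearly than the timing, but the stated timing puts such a patient at Days 44-56.

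A reader might also infer that the reassignment makes a cohort look complete at Day 43. SAP 8.1 tabulates discontinuations with reasons and the number of treatments by dosage group, and all data are listed, so the departure is visible.

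Nor does the rule hide toxicity. Treatment-emergent event tables, including events leading to discontinuation, do not use these visit labels. Worst site reactions through Day 43 and the worst-score ECOG shift table are unchanged, because the value stays within the same period. The ECOG shift table needs no amendment.

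**Conclusion.** The point holds as a minor defect in a stated rule. With Day 22 filled, safety data from a termination on Days 23-32 are tabulated as Day 43, 11 to 20 days off (11 to 17 days in the best-supported case). An early-termination ECG on Days 2-11 would likewise be tabulated as Day 22.

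This rests on nominal visit days, on the closest visit having valid data, and on reading the next available visit as the next later unfilled one. The one-third weight applies only to a cell of 3; the highest dose level is to have at least 6 evaluable patients.

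The reach is limited to descriptive by-visit safety tables. Site reactions are affected only if the site is assessed at termination, on which the protocol is not uniform: the synopsis lists it at end of study, while Table 1 and 5.5.2.7 do not. Immunologic data are outside the early-termination sentence. Coverage of PSA is unclear, but PSA velocity and doubling time are regressed on time and are not described as using visit labels. The MTD and DLT determination is outside the SAP (6.3) and is not touched.

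**What to change.** Replace the second sentence of SAP 7.4.7, and make the first subject to it, as follows in substance:

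- Early-termination data enter a scheduled visit only if the assessment date lies inside that visit's protocol window and the visit has no valid data for that variable.
- All other early-termination data appear in a separate *Early termination* row of the by-visit table, under the dose level last received.
- This rule takes precedence over the unscheduled and repeated laboratory rule in 7.4.6.
- State how it relates to the end of treatment phase visit in 7.4.5, so that one physical visit is not shown twice or under two labels.

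The cost is a short edit to 7.4.7, one extra row in the by-visit tables, and sometimes a smaller n at Day 43. Some values that the first sentence now places at a nearby visit would also move to the new row, for example terminations on Days 33-39, which are nearest to Day 43 but before its window opens. No data are lost, and each value is reported at a time it can support.

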7.4.8 Handling of Missing Values

Partial or Missing Dates

The following conventions will be used to impute missing portions of dates for AEs and concomitant medications. Note that the imputed values outlined here may not always provide the most conservative date. In those circumstances, the imputed value may be replaced by a date that will lead to a more conservative analysis.

- A. Start Dates
 - 1) If the year is unknown, then the date will not be imputed and will be assigned a missing value.
 - 2) If the month is unknown, then:
 - i) If the year matches the first dose date year, then impute the month and day of the first dose date.
 - ii) Otherwise, assign 'January.'
 - 3) If the day is unknown, then:
 - i) If the month and year match the first dose date month and year, then impute the day of the first dose date.
 - ii) Otherwise, assign the first day of the month.

B. Stop Dates

- 1) If the year is unknown, then the date will not be imputed and will be assigned a missing value.
- 2) If the month is unknown, then assign 'December.'

If the day is unknown, then assign the last day of the month.

Imputation

Missing data will not be imputed.

3)

7.4.9 **Pooling of Investigator Centers**

The data from all study centers will be pooled together for analysis.

7.4.10 Baseline Values

Baseline values are the values obtained prior to the first vaccination on Day 1. If the baseline value is missing, the value at Screening will be treated as the baseline.

8 Summary of Study Data

8.1 Subject Disposition and Dosing Summary

The tabulation of number of subjects in each dosage group and overall will be displayed for all subjects who are screened, in the Safety Population and in the Immunologic Population, respectively.

The number and percent of subjects who completed or discontinued the study will be displayed for each dosage group and overall together with reasons for early termination, where the percent is with respect to the total number of treated subjects in that dosage group. Similarly, the number and percent of subjects who completed or discontinued treatment will be displayed for each dosage group and overall together with reasons for treatment discontinuation.

The number of study treatments administered will be summarized by dosage group for the Safety Population.

8.2 Demographics and Baseline Characteristics

Subject demographic data and baseline characteristics will be summarized descriptively by dosage group and overall. The demographic data and baseline characteristics will be summarized for the Safety and Immunologic Populations.

Medical/oncology history and tumor burden evaluation data will be listed.

8.3 **Protocol Deviations**

All protocol deviations will be presented in a data listing.

8.4 **Prior and Concomitant Medications**

Prior and concomitant medications are defined in Section 7.4.5. The number and percentages of all concomitant medications will be summarized by dosage group, Anatomical Therapeutic Chemical (ATC) level 4 and PT. Subjects will be summarized through Day 43 using the assigned dose level as the treatment group. For additional treatment visits, follow up visits, and end of study, subjects will be summarized by cohort and by the dose level the subject took at the start date of the concomitant medication—this allows for subjects who changed their dose level to be summarized at the new dose level. The total number of concomitant medications and the number and percentages of subjects with at least 1 concomitant medication will be summarized by dosage group for the Safety Population.

Prior medications that are not concomitant will be listed but not tabulated.

8.5 Clinical Analysis

PSA will be summarized descriptively for each dosage group by visit for the observed value as well as for the change from baseline value (Day 1). Subjects will be summarized through Day 43 using the assigned dose level as the treatment group. For additional treatment visits, follow up visits, and end of study, subjects will be summarized by cohort and by the dose level the subject took at the visit immediately prior to the current visit—this allows for subjects who changed their dose level to be summarized at the new dose level.

PSA velocity (ng/mL/year) will be estimated by the slope of the least-square regression line fit to PSA versus time in years [1]. PSA velocity will be calculated using PSA values between Day 1 and Day 43, and subjects will be summarized using the assigned dose level as the treatment group. Also, to account for additional treatment visits, PSA velocity will be calculated using PSA values between Day 1 and the end of treatment phase visit, and subjects will be summarized by cohort and by the dose level the subject took at the last additional treatment visit. Finally, to account for follow up visits, PSA velocity will be calculated using PSA values between Day 1 and the end of study visit, and subjects will be summarized by cohort and by the dose level the subject took at the last treatment visit prior to the end of study.

PSA doubling time (months) will be estimated as follows for each visit range [1]:

- 1) Calculate the natural log-transform of all PSA observations [log(PSA)] in the visit range
- 2) Determine the slope of the least-square regression line of log(PSA) versus time in months of PSA measurement; convert the slope from years to months by multiplying the slope in years by the factor 12.
- 3) Divide the natural log of 2 [log(2)] by the slope calculated in step 2.

PSA doubling time will be estimated for 3 visit ranges: 1) up to and including Day 1 (baseline); 2) Day 1 through Day 43; 3) Day 1 through end of treatment phase visit; and 4) Day 1 through end of study. The baseline value will use all PSA values collected in the Medical History eCRF as well as any screening or Day 1 values in the safety laboratory data extract. For each post-baseline date range, each subject's PSA doubling time will be compared to their baseline value, and the number of subjects who have improved in the parameter (longer or negative doubling time) will be summarized, as well as the number of subjects who have not improved or who are worse (no change or shorter doubling time). For the summary from Day 1 through Day 43, subjects will be summarized using the assigned dose level as the treatment group. For Day 1 through end of treatment phase visit, subjects will be summarized by cohort and by the dose level the subject took at the last additional treatment visit and for Day 1 through end of study, subjects will be summarized by cohort and by the dose level the subject took at the last additional treatment visit and for Day 1 through end of study, subjects will be summarized by cohort and by the dose level the subject took at the last additional treatment visit and for Day 1 through end of study.

All PSA analyses will be conducted on the Safety Population.

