Treatment will be terminated with the 9th injection or will otherwise be terminated at any time upon the observance of PSA doubling < 90 days or occurrence of unacceptable toxicity. After termination, patients will be followed for an additional 6 months with monthly PSA levels and imaging studies as needed.

Once the MTD/RP2D is determined, patients receiving ongoing treatment may be escalated to that dose for subsequent treatments and receive a maximum of 9 injections. Patients who have received more than 9 injections due to the timing of the amendment limiting therapy to 6 months (9 doses), will be stopped at their last dose received and be followed for 6 months as with other patients. These subjects will continue to be followed for safety and biochemical PSA monitoring on a monthly basis for 6 months and are eligible to resume SNS-301 in case

of increases in PSA doubling to < 90 days or other evidence of disease progression and decline in immunological parameters.

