Dose-escalation will proceed once all patients in a cohort (unless the MTD is observed) have completed a 21-day safety evaluation following the first dose of study treatment in the cohort. Planned treatment may continue for an additional 2 extra doses of SNS-301 administered every 21 days. Additional patients will be enrolled at the highest dose level until at least 6 patients can be evaluated even if no DLTs are observed at the dose. In patients who tolerate SNS-301, additional treatment may be continued with single doses of SNS-301 at their current dose level to maintain geometric mean titer (GMT) of HAAH antibodies to no less than 4 times the baseline value for at least six months (9 injections). Treatment will be terminated with the 9th injection or will otherwise be terminated at any time upon the observance of PSA doubling < 90 days or occurrence of unacceptable toxicity as determined by the Investigator (either for that patient or in their dose cohort). After termination, patients will be followed for an additional 6 months with monthly PSA levels and imaging studies as needed.

Once the MTD/RP2D is determined, patients receiving ongoing treatment may be escalated to that dose for subsequent treatments and receive a maximum of 9 injections. Patients who have received more than 9 injections due to the timing of the amendment limiting therapy to 6 months (9 doses), will be stopped at their last dose received and be followed for 6 months as with other patients. These subjects will continue to be followed for safety and biochemical PSA monitoring on a monthly basis for 6 months and are eligible to resume SNS-301 in case of increases in PSA doubling to < 90 days or other evidence of disease progression and decline in immunological parameters.

Exploratory pharmacodynamic (PD) analysis will be performed using dose, vaccinespecific antibody response (geometric mean titer), antigen-specific T and B cell indices, and the relative expression of HAAH in each patient's tumor. The PD will be balanced and optimized to the degree of antigen-specific immune response and minimized for the production of regulatory immune processes. Safety endpoints will be evaluated by the incidence and severity of administration site reactions, changes in biochemical safety measures, general incidence and types of AEs, serious adverse events (SAEs), and other overt toxicities.

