10.1 List of Tables, Figures, and Listings

Table No.	Description of Table	Population
4.1.1	Subject Disposition	All Subjects
4.1.2.1	Demographics and Baseline Characteristics	Safety
14.1.2.2	Demographics and Baseline Characteristics	Immunologic
14.2.1.1	Study Treatment Administration Through Day 43	Safety
14.2.1.2	Study Treatment Administration by Additional Treatment Visit	Safety
14.2.2.1	Concomitant Medications Through Day 43	Safety
14.2.2.2	Concomitant Medications For Additional Treatment Visits	Safety
14.2.3.1.1	Change from Baseline in PSA by Visit Through Day 43	Safety
4.2.3.1.2	Change from Baseline in PSA by Additional Treatment Visit	Safety
14.2.3.2.1	Summary of PSA Velocity and PSA Doubling Time Through Day 43	Safety
14.2.3.2.2	Summary of PSA Velocity and PSA Doubling Time Through End of Treatment	Safety
14.2.3.2.3	Summary of PSA Velocity and PSA Doubling Time Through End of Study	Safety
14.3.1.1.1	Summary of Worst Administration Site Reactions Through Day 43 by Grade	Safety
14.3.1.1.2	Summary of Worst Administration Site Reactions For Additional Treatment Visits by Grade	Safety
14.3.1.2.1	Summary of Administration Site Reactions by Visit Through Day 43 and Grade	Safety
14.3.1.2.2	Summary of Administration Site Reactions by Additional Treatment Visit and Grade	Safety
14.3.2.1.1	Overall Summary of Adverse Events Through Day 43	Safety
14.3.2.1.2	Overall Summary of Adverse Events For Additional Treatment Visits	Safety
14.3.2.2.1	Treatment-Emergent Adverse Events (TEAE) by System Organ Class and Preferred Term Through Day 43	Safety
14.3.2.2.2	Treatment-Emergent Adverse Events (TEAE) by System Organ Class and Preferred Term For Additional Treatment Visits	Safety
14.3.2.3.1	Treatment-Emergent Adverse Events (TEAE) by System Organ Class and Severity Through Day 43	Safety
14.3.2.3.2	Treatment-Emergent Adverse Events (TEAE) by System Organ Class and Severity For Additional Treatment Visits	Safety
14.3.2.4.1	Treatment-Emergent Adverse Events (TEAE) by Preferred Term and Relationship to Study Treatment Through Day 43	Safety
4.3.2.4.2	Treatment-Emergent Adverse Events (TEAE) by Preferred Term and Relationship to Study Treatment For Additional Treatment Visits	Safety
4.3.2.5.1	Serious Treatment-Emergent Adverse Events (TEAE) by System Organ Class and Preferred Term Through Day 43	Safety
4.3.2.5.2	Serious Treatment-Emergent Adverse Events (TEAE) by System Organ Class and Preferred Term For Additional Treatment Visits	Safety

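### The late treatment-visit rows of the PSA change-from-baseline summary (SAP 8.5) cover only patients still being dosed, and fast PSA doubling ends dosing, so those rows tend to understate the PSA rise

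*SAP*

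**What the plan says.** **Summary.** SAP 8.5 states: "PSA will be summarized descriptively for each dosage group by visit for the observed value as well as for the change from baseline value". Through Day 43 patients are grouped by assigned dose. After that the rule is "For additional treatment visits, follow up visits, and end of study, subjects will be summarized by cohort and by the dose level" received at the visit just before. All PSA analyses use the Safety Population.

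**Stopping.** SAP section 4 says treatment ends with the 9th injection or is otherwise "terminated at any time upon the observance of PSA doubling < 90 days". Protocol 5.1 and 5.3.5 say the same. Protocol 5.2.3 puts a PSA doubling time under 90 days in a list introduced by "Other criteria for possible discontinuation are".

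**After stopping.** SAP section 4: "After termination, patients will be followed for an additional 6 months with monthly PSA levels". Both documents also allow dosing to resume during follow-up on evidence of progression.

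**Missing values.** SAP 7.4.8: "Missing data will not be imputed".

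**Tables.** SAP 7.4 sends follow-up assessments to listings only, unless the plan notes otherwise. 8.5 does note otherwise for PSA. Yet the only late by-visit PSA table in SAP 10.1 is 14.2.3.1.2, "Change from Baseline in PSA by Additional Treatment Visit". No PSA table by follow-up visit is listed.

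**The concern.** A patient who stops because his PSA is doubling quickly normally gives no value at later treatment visits. The patients left in those rows have been selected for slower PSA growth. Their mean change can flatten over time with no drug effect at all.

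The follow-up rows do not repair this. They are timed from the last dose, so one row holds early stoppers and nine-dose completers at quite different times since starting SNS-301.

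This summary is the SAP's display of PSA level over time. With 3 or 6 patients per dose level, a single exit can reshape a cohort's curve, and a reader could take the flattening as a sign of activity.

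**Working it through.** The plan gives no PSA effect, variance or stopping rate, so there is no figure of its own to reproduce.

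**1. Timing, from the visit schedule**
- Dose 9: Day 1 + 8 × 21 = Day 169.
- First follow-up visit, 28 days after the last dose: Day 22 + 28 = Day 50 after two doses, Day 43 + 28 = Day 71 after three, Day 169 + 28 = Day 197 after nine.
- The three-dose and nine-dose patients in that row are 197 − 71 = 126 days apart in time since Day 1.
- Last scheduled monthly PSA for a patient stopped after dose 1: Day 1 + 6 × 28 = Day 169. Scheduled PSA therefore reaches the day of dose 9 for every patient, whenever he stops.

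**2. One exit from a group of six (illustrative doubling times)**

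Fold-change at Day 169 is 2^(168 / doubling time in days). Take five patients at 9 months (about 274 days) and one who stops at 75 days.
- Each of the five: 2^(168/274) = 1.53. The stopper: 2^(168/75) = 4.72.
- All six: (5 × 1.53 + 4.72) / 6 = 2.06. Still dosed: 1.53.
- With the stopper at 89 or 60 days, the all-six mean is 1.89 or 2.44, again against 1.53.

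**3. Simulation with no drug effect**

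Assumptions not in the documents: log-linear PSA from 5 ng/mL; log-normal doubling time with log SD 0.5; log-scale measurement noise; automatic stopping once the least-squares doubling time from Day 1, on at least three values, is under 90 days. True doubling times are truncated at 3 months, following exclusion criterion 1. PSA is measured every 21 days to Day 169.

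| Median doubling time | Noise SD | Still dosed, Day 169 | Geometric mean fold, all / still dosed | Log rise understated | Mean change, still dosed ÷ all |
|---|---|---|---|---|---|
| 6 months | 0.1 | 81.5% | 1.90 / 1.77 | 11% | 0.87 |
| 6 months | 0.2 | 60.2% | 1.90 / 1.63 | 24% | 0.77 |
| 9 months | 0.1 | 89.8% | 1.59 / 1.54 | 7% | 0.90 |
| 9 months | 0.2 | 69.4% | 1.60 / 1.43 | 24% | 0.79 |

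The understatement is 1 − ln(still dosed) / ln(all). First row: 1 − ln 1.77 / ln 1.90 = 1 − 0.571 / 0.642 = 11%.

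A separate run over medians of 6 to 10 months and CV of 10 to 20% gave 9 to 39% of patients dropped and 7 to 24% understatement. At median 6 months and CV 15%, 30% were dropped and the apparent rise was 70% against a true 90%.

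**4. Sensitivity**
- No noise and no true doubling under 3 months: nobody stops, and the bias is zero.
- Log SD varied over 0.3 to 0.7 with noise 0.1 to 0.2, truncation kept: ratio of mean changes 0.74 to 0.97.
- Some patients truly doubling faster than 3 months on study (log SD 0.3 to 0.5): ratio 0.60 to 1.00.
- Rule read as PSA doubled from Day 1 within 90 days: understatement 1 to 11%.

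In none of these scenarios did the still-dosed rows show a larger rise than all patients. None of them models resumption.

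**The case against.** A reader might infer that 8.5 analyses PSA only in patients still on treatment, or that the trial's PSA endpoints are biased. The documents support neither. The sentence in 8.5 covers follow-up visits and end of study, and the population is everyone treated. The two clinical secondary endpoints, velocity and doubling time, are per-patient slopes calculated from Day 1 to end of treatment and again to end of study. Stopped patients stay in both, and doubling time is compared with each patient's own baseline.

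Other points against also carry weight:
- SAP 7.4 reports the number of non-missing values for continuous variables, and SAP 8.1 tabulates treatment discontinuation with reasons, so the loss can be seen. Neither shows what PSA did in those who left.
- The protocol plans no formal statistical analysis, and neither the MTD nor the RP2D depends on this table.
- Stopping need not be permanent. Resumed patients could re-enter treatment-visit rows and push the mean upward.
- If PSA doubling under 90 days is only a possible reason to stop, fewer patients leave. The value that triggers a stop may also still count at its own visit.
- The size rests on assumed inputs. With true doubling times truncated at 3 months, the simulated stops come from measurement noise.

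These limit the importance of the point and leave its size open. They do not give the treatment-visit rows a common time origin or an unselected set of patients.

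**Conclusion.** The point holds for the additional-treatment-visit rows of the by-visit PSA summary. They are conditional on continued dosing, dosing depends on PSA, and the SAP says nothing about it. The expected direction is an understated rise.

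A plausible size at Day 169 is 7 to 24% of the mean log rise, given a median doubling time of 6 to 10 months, log SD 0.5, truncation at 3 months, CV of 10 to 20% and automatic stopping. It can be zero, and resumption could reverse it. The documents cannot narrow this.

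It would go too far to say that stopped patients vanish from the PSA analysis: their values move to follow-up rows and remain in the slope endpoints. The table list is a separate, smaller fault: programmed as listed, it would omit the follow-up summary that 8.5 calls for. The summaries are descriptive, so no error rate or power is affected. This is a point to consider, not a barrier to using the plan.

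**What to change.** 1. Add a PSA change-from-baseline table for the Safety Population by assigned cohort and time since Day 1, to about Day 169. Use every collected value, including the monthly ones after treatment stops. State the windows and a rule for one value per patient per window, since 28-day windows over 21-day visits can hold two.
2. In each window show the numbers on treatment, off treatment, resumed, and on new anticancer therapy.
3. Keep Table 14.2.3.1.2 as supportive, labelled as conditional on continued dosing.
4. Align SAP 10.1 with 8.5, so that the follow-up and end-of-study PSA summary has a table.
5. Reconcile the passages that say treatment ends on PSA doubling under 90 days (Protocol 5.1 and 5.3.5, SAP section 4) with Protocol 5.2.3, which lists it as a possible criterion.

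The cost is SAP wording and one re-indexed table, with no new data collection: the protocol already says "patients will be followed for an additional 6 months with monthly PSA levels". The downside is that late windows mix on- and off-treatment values and depend on attendance at follow-up, from which patients may withdraw. The counts in item 2 make that visible.
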